Effect of PVP-I Nasal Sprays vs Normal Saline Nasal Sprays on
SARS-CoV-2 Nasopharyngeal Titers

NCT04347954

Document Date: July 10, 2020

Background Summary

Human transmission of SARS-CoV-2 (COVID-19) occurs primarily through droplet spread into the nose and mouth. Arresting COVID-19 replication after infection of the nasal tissues specifically would decrease the duration and severity of infection in COVID-19-exposed patients, and may significantly impact COVID human to human transmission. Povidone-iodine (PVP-I) solution is a widely available, inexpensive antiseptic medication, used in the surgical theater to reduce the incidence of surgical wounds and intranasally to reduce MRSA colonization. However, the role of PVP-I in the treatment of nasal infections is limited. Interestingly, prior in vitro studies have demonstrated dilute PVP-I solutions, in concentrations as low at 0.23%, produce a ≥ 4 log10 decrease (inactivation of $\geq 99.99\%$) in SARS and MERS virus titers within 15 seconds.^{1,2} Both viruses share high structural overlap with COVID-19. A study of 29 patients with recalcitrant sinusitis found reduced bacterial growth with good safety profile after use of 0.08% PVP-I nasal rinses.³ PVP-I nasal sprays of up to 4.4% concentration have also been used on healthy volunteers without adverse effects or nasal tissue damage.⁴ In Wuhan, China, PVP-I was recently used empirically by healthcare providers devoid of COVID-19 protection, given its ease of use, and potential for mitigating infection. Given this encouraging background, and current world events, we propose testing dilute PVP-I sprays as a topical treatment to directly ablate COVID infection within the nasal cavity.

Specific aims

1. To determine if PVP-I nasal sprays reduce viral shedding in the nasopharynx and nasal cavity
 - a. Hypothesis 1: PVP-I nasal sprays will reduce viral shedding in the nasopharynx and nasal cavity as determined by PCR testing when compared to control groups
2. To determine if PVP-I nasal sprays affect the severity and time to resolution of signs and symptoms of COVID-19
 - a. Hypothesis 2a: PVP-I nasal sprays will not change the severity or time to resolution of systemic signs and symptoms (such as fever, fatigue) when compared to control groups
 - b. Hypothesis 2b: PVP-I nasal sprays will reduce the duration of anosmia symptoms when compared to control groups
3. To determine adverse effects of PVP-I nasal sprays

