 - a. Hypothesis 3: PVP-I nasal sprays will not be associated with a greater rate of adverse effects as compared to the control groups

Methods

Overview of study design

This is a prospective, double-blind, placebo controlled, randomized control trial of COVID-19 positive patients that has three study arms.

Arms:

- (1) 2% povidone iodine nasal spray – two sprays to each nare four times a day for 5 days
- (2) 0.5% povidone iodine nasal spray – two sprays to each nare four times a day for 5 days
- (3) Control – Dyed normal saline (0.9% NaCl) spray – two sprays to each nare four times a day for 5 days

Study population: COVID-19 positive inpatients and outpatients

Inclusion criteria:

1. ≥ 18 years ago
2. Diagnosis of COVID-19 by lab test within 5 days of study participation

Exclusion criteria:

1. Allergy to "iodine," shellfish, or food dye
2. Receiving intranasal steroids
3. Sinus surgery within 30 days of beginning the study
4. Intubated at the time of enrollment
5. Pregnancy
6. Participation in other COVID-19 studies - to be determined on a case by case basis

Measurements/Outcomes

The primary outcome measure is the viral load on nasopharyngeal swab determined by quantitative PCR testing. A baseline sample (Day 1) will be obtained prior to first administration of the sprays. Subsequent samples will be collected at 4 hours after first administration and on day 5 after initiating nasal sprays.

Intake questionnaire – dates of symptom onset, comorbid conditions, specific questions regarding taste and smell disturbances

Patient reported symptoms (completed on Day 3 and Day 5) – fever, fatigue, change or loss of sense of smell, change or loss of sense of taste, nasal congestion, sore throat, etc

Adverse effects questionnaire (completed on Day 3 and 5) – Nasal burning/pain, headaches, ear pain, sneezing, nose bleeds, rash

University of Pennsylvania Smell Identification Test (completed on day 1 and day 30) – to assess smell recovery in COVID-19 patients

Statistics

T-test or ANOVA to compare difference in mean viral load between groups. Chi-square to assess for differences in signs, symptoms, adverse effects.

Sample size: 45 subjects (15 subjects per study arm)

Study Procedures - Outpatient

Recruitment strategy

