We have also received approval from [name] who is the Operations Manager of the Galvez research lot to utilize the tent space or the parking lot space at this site for study procedures. Weekday study procedures will take place at this site ([name]).

Participants will complete the first questionnaire and take the University of Pennsylvania Smell Identification Test (UPSIT) on the day of enrollment. This is a multiple-choice scratch and sniff test that is self-administered. A baseline nasopharyngeal sample will be taken. Next the first dose of the nasal spray will be given. Subjects will have the option to stay or return for the four hour sample collection timepoint. Four hours later, a member of the research team will obtain the 4-hour post-administration nasal sample. Subjects will then return home. Participants will be given (physical or electronic) a gift card for \$25 at the end of the day.

Participants will continue to self-administer the spray as instructed while at home. They will also take daily symptom questionnaires administered through REDCap. Participants will return for a drive-through nasal swab at [name] or at the Galvez lot on Day 5.

On day 30, participants will complete an UPSIT, self-administered smell test, which will be given to patients with a self-addressed, pre-paid envelope to return.

Close Out

The study medication will be discontinued on Day 5. The second gift card (\$25) will be mailed either through the postal service or through email to participants approximately 30 days after the first study visit upon completion of the final UPSIT.

Specimen Handling

Each sample will be labelled with a subject's unique record ID number. These samples will be processed in the Stanford clinical virology lab (permission has been obtained from [name]) and results associated with a given record ID number in REDCap.

Payment/Reimbursement

Participants will be given a total of \$50 in gift cards if they complete the study. They will receive a \$25 gift card at the end of the first in person study visit. If they complete the remaining in person visits on Days 5, they will be mailed (either via postal service or email) the second \$25 gift card along with the final smell test.

Safety of proposed treatment arms

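### The adverse-effects form as described names six items with no field for other or serious events, and a participant too ill to respond has no recorded outcome

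*Combined protocol and SAP*

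**What the plan says.** All references are to the combined protocol and SAP.

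- **Adverse effects.** Methods, Measurements/Outcomes, describes a questionnaire given on Day 3 and Day 5 and lists its content as "Nasal burning/pain, headaches, ear pain, sneezing, nose bleeds, rash". The list has no entry for other events, and no grade or seriousness is mentioned.
- **Symptoms.** In the same section the patient-reported symptom list is open-ended: "fever, fatigue, change or loss of sense of smell, change or loss of sense of taste, nasal congestion, sore throat, etc". For outpatients, the Active Phase text adds: "They will also take daily symptom questionnaires administered through REDCap".
- **Population.** Methods gives it as "COVID-19 positive inpatients and outpatients". Intubation appears once, among the exclusion criteria: "Intubated at the time of enrollment".
- **Safety hypothesis.** Hypothesis 3 reads "PVP-I nasal sprays will not be associated with a greater rate of adverse effects as compared to the control groups". The Statistics section plans a chi-square test for signs, symptoms and adverse effects, with 15 participants in each of three arms.
- **Not stated anywhere.** There is no definition of a serious event. Nothing collects emergency care, admission, intubation or death. There is no rule for withdrawal, loss to follow-up or missing data.

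**The concern.** Hypothesis 3 predicts no excess of adverse effects, so an event that is not recorded moves the result towards the prediction. The trial enrols people with active COVID-19, some already in hospital, and the exclusion for intubation shows that severe illness was foreseen. Iodine, shellfish and food-dye allergy are exclusions, yet rash is the only listed item that could point to an allergic reaction.

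Two kinds of participant fall through:

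1. One who worsens but still answers. The worsening can appear on the symptom form, but the adverse-effects form as described has no place for it.
2. One who can no longer answer or come for the Day 5 swab. The plan describes no fallback contact and no way to record what happened.

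At stake is whether a finding of no excess means that no serious events occurred or only that none were asked about. The gap lies within the spray days and does not depend on how long follow-up lasts.

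**Working it through.** **1. What each source can record, as described**

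| Event during the spray days | Adverse-effects form | Daily symptom form | Any other source |
|---|---|---|---|
| One of the six listed items | Yes | Possibly | None described |
| Other new problem, participant answers | No field | Only as a symptom | None described |
| Emergency care or admission, participant answers | No field | Only the symptoms, not the care received | None described |
| Intubation, death or similar incapacity | No | No | None described |

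**2. Inputs**

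- 15 per arm and 45 in total (Statistics). 3 × 15 = 45 is consistent. No power, event rate or dropout is given, so the plan has no further figure to reproduce here.
- The number of deteriorations is not in the documents. I take k = 1, 2 or 3 in one arm as illustrations. A range of 3% to 15% of all participants, also an assumption, would be 45 × 0.03 = 1.35 to 45 × 0.15 = 6.75, or about 1 to 7 people.

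**3. Counted versus left out**

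For k events in n, the exact (Clopper-Pearson) 95% limits are the 0.025 quantile of Beta(k, n − k + 1) and the 0.975 quantile of Beta(k + 1, n − k). For zero events the upper limit is 1 − 0.025^(1/n). The last two columns assume that the k participants are dropped from the table.

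| k | Counted, k/15 (95% interval) | Left out | Upper limit if left out |
|---|---|---|---|
| 1 | 6.7% (0.2% to 31.9%) | 0/14 | 23.2% |
| 2 | 13.3% (1.7% to 40.5%) | 0/13 | 24.7% |
| 3 | 20.0% (4.3% to 48.1%) | 0/12 | 26.5% |

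If the participants stay in the denominator because they answered the form, but the form has no field for the event, the arm reads 0/15 (upper limit 21.8%).

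**4. Would counting them change a test?**

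For k/15 versus 0/15, the two-sided Fisher p is 2 × C(15,k)/C(30,k):

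- k = 2: 2 × 105/435 = 0.48
- k = 3: 2 × 455/4060 = 0.22
- k = 4: 2 × 1365/27405 = 0.10
- k = 5: 2 × 3003/142506 = 0.042

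Five events against none are needed to pass 0.05. The uncorrected chi-square would already give p = 0.032 at k = 4. But the expected event count per arm is then 15 × 4/30 = 2, too small to rely on that test.

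**5. Chance that the gap is ever exercised**

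The probability of at least one event in an arm of 15 is 1 − (1 − p)^15. At assumed rates of 1%, 2%, 5% and 10% it is 14%, 26%, 54% and 79%. For all 45 participants it is 36%, 60%, 90% and 99%.

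**The case against.** The strongest reply is that the form itself is not in the documents. The six items come from a one-line summary. The participant timeline describes a form that also covers compliance, so it holds more than the six items and may have an open field. This stands as a limit: the point concerns the form as described. If an open field exists, the plan should say so. It would still leave the participant who cannot answer.

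A reader might infer more than the documents support, in four ways:

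- **That any participant who deteriorates becomes missing data.** No complete-case rule is written, and nothing says that forms already completed are discarded. Someone who worsens but answers is on the daily symptom form. Admission alone does not prevent a REDCap entry, and the trial itself foresees people in hospital. The inability is secure only for intubation, death or similar incapacity.
- **That an inpatient is lost by missing the drive-through visit.** That visit is described for outpatients. Inpatient procedures are not described, so for inpatients the plan is silent on capture.
- **That the list holds only mild local complaints.** Headache and rash are not local, and no severity is stated for any item.
- **That the severity comparison fails as well.** Aim 2 is "To determine if PVP-I nasal sprays affect the severity and time to resolution of signs and symptoms of COVID-19", and Hypothesis 2a concerns systemic signs and symptoms such as fever and fatigue. Treating admission or intubation as severity outcomes would be a design preference.

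It is also fair to say that most such events would probably reflect COVID-19 and not the spray. Adding them to the adverse-effect count would blur both, so they need a separate outcome.

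**Conclusion.** The point holds in this form: the described questionnaire has no field for other or serious events, no part of the plan collects emergency care, admission, intubation or death, and no rule covers a participant too ill to respond. Followed as written, Hypothesis 3 could be reported as supported with serious events during the spray days uncounted.

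The size rests on assumed counts. One to three such participants in an arm of 15 would be a true 6.7% to 20.0% shown as 0%, provided that they are left out or the form has no place for the event. The gap itself does not depend on a rate, since one participant is enough. The value of closing it is descriptive: a difference of 2/15 against 0/15 would not change a formal conclusion. It should be corrected, but it does not undermine the viral-load comparison or the data on the six listed items.

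**What to change.** 1. Add two items to the existing Day 3 and Day 5 forms: a free-text *any other new problem*, and *emergency care, hospital admission, higher level of care or intubation since the last form*. If the form already has an open field, state that in Measurements/Outcomes.
2. If a form or the Day 5 swab is missed, have the team phone the participant or a contact, or check the chart for inpatients. Record the reason and the participant's status, including death.
3. Report these events by randomised arm as a separate serious-event outcome, with all randomised participants as the denominator and exact intervals. Keep the table descriptive and apart from the six local and tolerability items, so that disease progression is not mixed with effects of the spray.
4. Align the day labels while editing. The timeline puts this form on Days 2 and 4, probably because it counts enrolment as Day 0.

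The cost is two form items and a few calls by a team that already phones participants at screening. Sample size, visits and the primary outcome are unchanged. Reported event counts will be higher, most of them likely due to COVID-19, and with 15 per arm the table gives no formal power.

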In terms of advertising to the general public, we will send out flyers for general distribution on social media (e.g., Facebook, Nextdoor, etc) that will allow interested persons in the general public to contact our team. Our social media advertising strategy is being developed in conjunction with StudyPages, a clinical trial recruitment company recommended by the Stanford Research Participation Program.

Moderation of Facebook and other social media posts will be conducted as outlined in a separate

attached document and includes daily monitoring of comments and hiding/deletion of protected health information. Prospective participants can opt to have their contact information sent to the team.

Potential subjects who have expressed interest in being contacted about research studies will be contacted by phone by one of the investigators. The study will be described, patients will have the opportunity to ask questions, and if they wish to proceed, they will be given details on their first in person study visit.

Prospective participants that have undergone telephone screening will come to the clinic parking lot at [name] or the Galvez lot at the designated date and time. At this in person study visit, the study will be reviewed again and the consent form signed if the patient still wishes to proceed. Randomization will take place. This will count as Day 1 of the study.

Active Phase

Given the known COVID-19 positive status, we are putting in place the following procedure for in person study visits. For first study visits scheduled on a Saturday, subjects will drive to the [name] parking lot which is the parking lot associated with the Department of Otolaryngology's clinics. We have approval from the department chair and clinic leadership to use the parking lot. Participants will remain in their vehicle with the window rolled down for necessary study procedures. Return visits on day 5 will be scheduled for times either before 8 am or after 5 pm. Privacy will be ensured in several ways. First, the parking lot is behind the building and thus not visible from the main road. Second, we will be using moveable plastic barriers during study procedures to protect privacy. Lastly by having subjects only come in outside normal clinic hours (Saturday or pre/post-clinic), this will minimize the presence of other persons.

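### The primary viral-load analysis names no scale, no primary post-dose sample and no use for the pre-dose PCR value; log-scale ANCOVA at one named sample closes all three gaps by wording alone

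*Combined protocol and SAP*

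**What the plan says.** The combined protocol and SAP defines the endpoint under Measurements/Outcomes: "The primary outcome measure is the viral load on nasopharyngeal swab determined by quantitative PCR testing". Three samples follow from that section: "A baseline sample (Day 1) will be obtained prior to first administration of the sprays", then "Subsequent samples will be collected at 4 hours after first administration and on day 5 after initiating nasal sprays". Active Phase repeats the pre-dose sample ("A baseline nasopharyngeal sample will be taken"). The planned analysis, under Statistics, is "T-test or ANOVA to compare difference in mean viral load between groups", with 15 subjects in each of three arms.

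Nothing elsewhere adds a scale, a primary time point, a covariate or a rule for undetectable results. The only log scale is in the Background Summary, where it describes in vitro work ("produce a ≥ 4 log10 decrease") and not the trial outcome.

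Two labels also differ between sections. Recruitment strategy says of the first visit that "This will count as Day 1 of the study", and the last swab is then on day 5. The Participant study timeline puts the same events at Day 0 and Day 4. Active Phase calls the baseline sample nasopharyngeal and both later samples nasal; the timeline calls all three NP.

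**The concern.** Each gap leaves a choice that could be made after the data are seen.

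- **Scale.** The sentence permits a mean of raw copies. If viral load is roughly log-normal, a few very high values dominate that mean and most of the power goes.
- **Sample.** Two post-dose samples and two PVP-I v saline comparisons give up to four candidate primary tests, so a positive result at either sample could be presented as the primary one.
- **Baseline.** A pre-dose value is scheduled for every participant, but the analysis gives it no role. With 15 per arm precision is scarce, and an unused predictor of the outcome may be a lost opportunity.

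**Working it through.** **Inputs from the document:** three arms, 15 per arm, one pre-dose and two post-dose PCR samples. The stated total reproduces only as 3 x 15 = 45. No alpha, power, effect size, SD or correlation is given, so it cannot be derived further.

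**Assumptions (not in the document):** log-normal load, log10 SD 1 to 2, true 1-log10 reduction, two-sided 5%, no dropout.

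**1. Precision.** SE of one PVP-I v saline difference = SD x sqrt(2/15) = 0.365 x SD. The 95% CI half-width is 2.048 x 0.365 x SD, which is 0.75 log10 at SD 1 and 1.50 log10 at SD 2.

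**2. Scale.** The noncentrality on log10 is 1/(0.365 x SD), with 28 df. Raw-copy power comes from 20,000 simulated trials.

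| SD | Noncentrality | Power, log10 | Power, raw copies |
|---|---|---|---|
| 1 | 2.74 | 75.3% | 17.9% |
| 1.5 | 1.83 | 42.2% | 3.7% |
| 2 | 1.37 | 26.2% | 1.1% |

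A cycle threshold that is linear in log10 (about 3.3 cycles per log10 at perfect doubling) gives the same p-values as log10.

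**3. Sample.** Chance of at least one false positive when both samples are tested at 5% (40,000 null trials per setting):

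| Correlation between samples | One omnibus ANOVA per sample | Four unadjusted pairwise contrasts |
|---|---|---|
| 0.3 | 9.3% | 17.0% |
| 0.5 | 9.1% | 15.9% |
| 0.7 | 8.4% | 15.0% |

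Two unadjusted contrasts at a single sample give about 9.0%.

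**4. Baseline.** The expected variance of the ANCOVA contrast, relative to the unadjusted post-dose contrast, is (1 - r^2) x [1 + 1/(f - 2)]. Here r is the baseline correlation and f the within-arm degrees of freedom.

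- Two arms: f = 28, factor 1 + 1/26 = 1.038, break-even r = sqrt(1/27) = 0.19 (0.20 allowing for the t critical value).
- Three arms: f = 42, factor 1 + 1/40 = 1.025, break-even r = sqrt(1/41) = 0.16.
- With losses to 10 per arm (assumed): 0.24 and 0.20.

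Pairwise power, ANCOVA with 27 df:

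| r | SD 1 (unadjusted 75.3%) | SD 2 (unadjusted 26.2%) |
|---|---|---|
| 0 | 73.6% (-1.7) | 25.4% (-0.8) |
| 0.3 | 77.5% (+2.2) | 27.4% (+1.2) |
| 0.5 | 84.9% (+9.6) | 32.2% (+6.0) |
| 0.7 | 95.2% (+19.9) | 44.2% (+18.0) |

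If a change from baseline was meant, its variance ratio to the post-dose comparison is 2(1 - r), assuming equal variances. ANCOVA is then more precise while (1 + r) x factor / 2 < 1. That means r below 2/1.038 - 1 = 0.93 (two arms) or 2/1.025 - 1 = 0.95 (three arms).

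**5. Undetectable results.** Assume 30% of saline follow-up values fall below the limit and the baseline mean is 1 log10 higher. Setting such values to the limit and running log10 ANCOVA (15 v 15, 20,000 trials per cell) gave type I error of 4.7%-5.2%. Power from SD 2 to SD 1 was 23%-63%, 26%-69% and 34%-80% at r = 0.3, 0.5 and 0.7. Rank-based ANCOVA gave 24%-67%, 27%-73% and 34%-84%.

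Substitution shrinks the estimate. The mean of max(Y, L) is mu + SD x [h x Phi(h) + phi(h)], with h = (L - mu)/SD.

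- SD 1: L = -0.524, saline mean 0.190, PVP-I mean -0.319, difference 0.51.
- SD 2: L = -1.049, saline mean 0.381, PVP-I mean -0.226, difference 0.61.

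So in this setting a true 1-log10 difference appears as about 0.5 to 0.6.

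**The case against.** The strongest reply is that nothing planned is invalid. Under randomisation an unadjusted log10 comparison of post-dose values is a legitimate test, so the baseline point is about efficiency, not error. That stands. With no documented correlation, the gain may be trivial.

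Three further replies carry weight.

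- With three arms, ANOVA is a natural reading of the sentence, and then the false-positive figure is about 8%-9%. A reader might infer that the plan carries a 15%-17% error rate; that is only the upper end, for four unprotected contrasts.
- The laboratory may report cycle thresholds, in which case the scale problem disappears. A reader might infer that the trial would be analysed on raw copies with almost no power. The document permits that but does not say it.
- The sponsor may have intended a change from baseline. The sentence reads more naturally as a between-group contrast of means, and ANCOVA is the more precise choice against either reading unless the correlation is very low (post-dose) or very high (change).

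It is also tempting to read the day labels as two different swab dates, or *nasal* as a change of sampling site. The labels fit a one-day numbering offset, and *nasal* may be shorthand, since the outcome definition and the timeline both specify nasopharyngeal swabs. These are points to reconcile, not evidence of a flaw in the analysis.

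What survives is the omission itself: no section names the scale, the primary sample, the role of baseline or the handling of undetectable results.

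**Conclusion.** The concern holds as an under-specified primary analysis that should be fixed; confidence is medium. The gaps are plain in the text. Their size depends on assumptions.

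Scale has the largest potential effect: 1%-18% power on raw copies against 26%-75% on log10, and no effect if cycle thresholds are reported. The open choice of sample comes next: about 8%-9%, and up to 15%-17%, chance of a false positive. Baseline adjustment is a smaller, conditional gain: 1-2 power points at correlation 0.3, 6-10 at 0.5, 18-20 at 0.7, and a loss of 1-2 at zero.

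These figures rest on an assumed SD, effect and correlation; they show sensitivity, not this trial's actual loss. A reader might infer that adjustment rescues a trial of 15 per arm. It does not: at SD 2 and correlation 0.5, power is still only 32%.

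**What to change.** Replace the viral-load sentence under Statistics with:

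> The primary analysis compares log10 viral load (or cycle threshold, if that is what the laboratory reports) at one post-dose sample named in advance by the sponsor, using ANCOVA with arm as a three-level factor and the pre-dose value on the same scale as covariate. Each PVP-I minus saline difference is reported with a 95% CI. The other post-dose sample is secondary. Values below the assay limit are set to the limit in the primary analysis. A rank-based ANCOVA (ranks within the two arms compared) and a Tobit model, with degrees of freedom based on the number of participants actually analysed, are sensitivity analyses.

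Add two statements.

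- Setting undetectable values to the limit shrinks the estimated difference towards zero and, at 30% undetectable, costs about 1-5 power points against ranks, with type I error staying near 5%.
- Whether the two PVP-I v saline contrasts are adjusted for multiplicity. Unadjusted, the family-wise error is about 9%. Dunnett in the three-arm ANCOVA brings it to 5% for about 3-10 power points per contrast.

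Before naming the sample, reconcile the day labels (Day 1/Day 5 v Day 0/Day 4) and the *nasal* v *nasopharyngeal* wording.

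Cost: wording only, with no new samples, visits or participants. The downside is about one residual degree of freedom, and 1-2 power points if the baseline correlation is near zero.

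### The primary viral-load comparison makes no use of the symptom-onset date collected at intake, so variation in illness day stays in the error term: a modest, conditional loss of precision, not a bias

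*Combined protocol and SAP*

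**What the plan says.** All of the following is in the Methods of the combined protocol and SAP, unless another section is named.

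- **Outcome.** Under Measurements/Outcomes: "The primary outcome measure is the viral load on nasopharyngeal swab determined by quantitative PCR testing". The scale (raw, log10 or cycle threshold) is not given, and no primary timepoint is named.
- **Sampling.** "A baseline sample (Day 1) will be obtained prior to first administration of the sprays", and then "Subsequent samples will be collected at 4 hours after first administration and on day 5 after initiating nasal sprays". The use of the pre-dose value in the analysis is not stated.
- **Analysis.** Under Statistics, one sentence covers the primary outcome: "T-test or ANOVA to compare difference in mean viral load between groups". No covariate or model is named.
- **Illness timing.** The intake questionnaire asks for "dates of symptom onset, comorbid conditions". The outpatient Active Phase text places the first questionnaire ahead of the baseline swab and the first spray. No stated analysis uses the onset date.
- **Entry.** "Diagnosis of COVID-19 by lab test within 5 days of study participation". No criterion concerns days since onset. "Study population: COVID-19 positive inpatients and outpatients".
- **Allocation.** The outpatient recruitment text says "Randomization will take place" and gives no stratification factor.

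**The concern.** Viral load in the nasopharynx can be expected to depend on how far the illness has run. Entry is tied to the test date, so two participants tested on the same day may have had symptoms for quite different lengths of time. The spread may be wider with both inpatients and outpatients eligible.

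Neither the design nor the analysis removes that variation: allocation is not described as stratified, and the test has no covariates. With 15 per arm, precision is scarce, and the trial already holds a pre-treatment variable that might recover some of it.

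The onset date can also carry information that the pre-dose swab does not. One swab gives a level on one day. Participants with the same level, one early and one late in the illness, could differ by Day 5. At stake is some power for each PVP-I versus saline comparison, and some protection against choosing a covariate after seeing an imbalance.

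**Working it through.** **The plan's own figure.** 3 arms x 15 = 45, which agrees with the stated total. The 45 cannot be derived further, because no alpha, power, effect size or SD is given.

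**Inputs.** From the documents: n = 15 per arm, three arms. Assumed, because the documents are silent: two-sided 5% test of one PVP-I arm against saline, no dropout, no multiplicity adjustment, and effects of 0.73 to 1.0 SD of log10 viral load. Rho, the correlation of illness day with the viral load analysed, is varied from 0 to 0.5.

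**Starting precision.** A two-arm t-test with 15 per arm (28 df) has 80% power at a difference of 1.06 SD.

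**Formula.** With k covariates explaining a share R² of within-arm variance, residual df = 42 - k. The variance of the difference, in unadjusted SD units, is (2/15) x (1 - R²) x [1 + k/(41 - k)]. The last factor allows for chance covariate imbalance: 1 + 1/40 for k = 1, 1 + 2/39 for k = 2, 1 + 3/38 for k = 3. Power comes from the noncentral t with noncentrality equal to effect / sqrt(variance).

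**Step 1: onset day added to the unadjusted plan.** Unadjusted power is 0.497 at 0.73 SD and 0.763 at 1.0 SD. R² = rho². The indicator for participants without symptoms is assumed to explain nothing.

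| rho | onset only (k = 1), 0.73 / 1.0 SD | onset + indicator (k = 2), 0.73 / 1.0 SD |
|---|---|---|
| 0 | -0.010 / -0.011 | -0.020 / -0.022 |
| 0.2 | +0.006 / +0.006 | -0.004 / -0.005 |
| 0.3 | +0.027 / +0.028 | +0.017 / +0.017 |
| 0.4 | +0.060 / +0.059 | +0.049 / +0.049 |
| 0.5 | +0.108 / +0.099 | +0.096 / +0.090 |

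The right-hand column is the relevant one, because the workable model needs the indicator.

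**Step 2: onset day added when the pre-dose PCR value is already in the model.** Take an effect of 0.75 SD and baseline-to-follow-up correlation r. Assume onset day has the same correlation q with pre-dose and follow-up load. Then R² = (r² + q² - 2rq²)/(1 - q²). At r = 0.5, power is 0.519 unadjusted and 0.628 with the pre-dose value (k = 1).

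| q | R² (r = 0.5) | partial rho | gain, onset (k = 2) | gain, onset + indicator (k = 3) |
|---|---|---|---|---|
| 0.3 | 0.275 | 0.18 | +0.003 | -0.009 |
| 0.4 | 0.298 | 0.25 | +0.017 | +0.005 |
| 0.5 | 0.333 | 0.33 | +0.040 | +0.028 |

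At r = 0.7 the k = 2 gains are -0.004, +0.003 and +0.013. The pre-dose value itself is worth 0.628 - 0.519 = 0.109 at r = 0.5, more than onset adds after it.

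**Step 3: what rho might be.** If load changes by b log10 per day and illness day has SD s, then R² = (bs)²/[(bs)² + e²], where e is the SD from other sources. A middle assumption (b = 0.2, s = 2.5 days, e = 1.5) gives 0.25/(0.25 + 2.25) = 0.10, so rho is about 0.32. Over b = 0.1 to 0.3, s = 1.5 to 4 and e = 1.0 to 2.0, R² runs from about 0.01 to 0.59. None of these values is in the documents.

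**Step 4: chance imbalance.** The difference in mean illness day between two arms has SD s x sqrt(2/15) = 0.365s. That is 1.1 days at s = 3 and 1.5 days at s = 4, or about 0.2 to 0.3 log10 at b = 0.2.

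**Step 5: timepoint.** At b = 0.2 log10 per day, the change over 4 hours is 0.2 x 4/24 = 0.03 log10. The argument about rising or falling load therefore bears on Day 5, not on the 4-hour sample.

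**The case against.** The strongest case against is that the deciding quantity is missing. Nothing in the documents supports rho of 0.4 or more, and the middle assumption in Step 3 (rho about 0.32) yields only about 2 points with the indicator. Once the pre-dose swab is modelled, most of the gain goes. On this view the real gap is the unstated use of the baseline value, and onset day only refines it. That stands, and it is why the remedy below puts both in one model.

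Three further points also stand.

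- The plan's wording does not exclude change from baseline, under which part of the illness-day variation would cancel, especially at 4 hours.
- The 5-day test window may narrow the spread of illness day indirectly, so an SD of 3 to 4 days is only an assumption.
- If load rises and then falls, a single linear term captures the course imperfectly.

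A reader might go further the other way and infer that the unadjusted comparison is biased or invalid, because arms can differ by chance on illness day. The documents do not support that. Allocation is randomised, and the unadjusted standard error already includes this variation. A reader might also infer a dependable gain of about 10 points; that needs rho of 0.5 and no adjustment for the pre-dose value.

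What the objection does not remove is that the variable is already collected, is measured before treatment in the outpatient sequence, and has no stated use.

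**Conclusion.** The point holds as a low-cost efficiency refinement. The documents confirm an unadjusted primary test, a recorded onset date, no entry limit on days since onset and no described stratification. The consequence is lost precision.

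The loss is negligible if rho is 0.2 or less and reaches about 5 points of power only near rho 0.4. It is smaller still beside a pre-dose PCR term: about 0 to +4 points for rho 0.3 to 0.5, or -1 to +3 with the indicator. These figures rest on 15 analysed per arm, a two-sided 5% test without multiplicity adjustment and, for the last range, baseline correlation 0.5 and equal onset correlations. If onset predicted Day 5 load more strongly than pre-dose load, the added gain would be larger; the documents neither show this nor rule it out. Priority is low, and confidence in a material gain is low.

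**What to change.** In the Statistics section, replace the single sentence on the primary outcome with a prespecified linear model for log10 viral load. Its terms would be arm, pre-dose PCR value, and days from symptom onset to first spray as a linear covariate. For participants without symptoms, use the date of the positive test in place of the onset date, plus an indicator, so that nobody is dropped. Keep the unadjusted comparison as a sensitivity analysis, and state that the onset term is expected to help mainly at Day 5.

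The cost is a sentence or two of analysis text, with no new data or visits. The onset terms use one or two degrees of freedom, worth up to about 2 points of power if onset is unrelated to viral load. Recalled onset dates carry error, which would weaken any gain.
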